8.2.2.2. Hepatotoxicity

In addition, a more detailed summary of hepatobiliary laboratory abnormalities will be provided for liver function tests, including ALT, ALP and total bilirubin. A listing of which subjects met each Hepatobiliary laboratory criteria post-baseline will also be produced.

A graphical presentation of maximum ALT (x ULN) versus baseline ALT (x ULN) value for each subject on treatment will be produced.

A graphical presentation of maximum total Bilirubin (x ULN) versus maximum ALT (x ULN) values on treatment will be produced.

8.2.3. Overview of Planned Other Safety Analyses

The safety analyses will be based on the “Safety” population, unless otherwise specified.

Table 8 provides an overview of the planned analyses, with further details of data displays being presented in [Appendix 13: List of Data Displays](#).

Table 8 Overview of Planned Other Safety Analyses

Endpoint / Parameter/ Display Type	Absolute			Change from BL		
	Summary		Individual	Summary		Individual
	T	F	L	T	F	L
ECG						
ECG Findings	Y					
Change from Baseline in ECG Values by Visit				Y		
ECG Results by PCI Criteria	Y					
QTcF and QTcB Values by Visit and Category	Y					
Change from Baseline in QTcF and QTcB Values by Visit and Category				Y		
Abnormal ECG Findings			Y			
All ECG Data for subjects with any value of PCI			Y			
Vital Signs						
Change from Baseline in Vital Signs by Visit				Y		
Vital Signs Results by PCI Criteria	Y					
All Vital Signs for subjects with any value of PCI			Y			

NOTES:

- T = Table, F = Figures, L = Listings, Y = Yes display generated, PCI = Potential Clinical Importance
- Summary = Represents TFL related to any summaries (i.e. descriptive statistics) of the observed raw data.
- Individual = Represents FL related to any displays of individual subject observed raw data.

8.2.3.1. Vital Signs

The vital signs summary will be based on recordings of systolic blood pressure (mmHg), diastolic blood pressure (mmHg), and heart rate (bpm). Note: weight is assessed as part of efficacy.

The number of subjects with vital sign results relative to the potential clinical importance criteria will be summarised by test and category. Data will be summarised by visit, including ‘any on-therapy visit’ and ‘any post-baseline visit’. The criteria for vital signs of potential clinical importance are detailed in Section 11.7.3.

8.2.3.2. Electrocardiograms

ECG parameters will be collected in triplicate at each time point including heart rate, QRS interval, QT interval, QT interval – Bazett correction (QTcB), QT interval – Fredericia correction (QTcF), RR interval and PR interval. The mean of the triplicate measurements will be calculated for each ECG parameters and used in any derivation of summary statistics. For ECG findings and PCI criteria, all three ECGs will be considered and the worst case result will be summarised. The baseline value used for assessing PCI will be the mean of the triplicate measurements.

The number of subjects with ECG values of potential clinical importance will also be summarised. Data will be summarised by visit, including ‘any on-therapy visit’ and ‘any post-baseline visit’. The criteria for ECG values of potential clinical importance are detailed in Section 11.7.2. A summary of the number and percentage of subjects in overall ECG interpretation and abnormal findings will be displayed by treatment group over time.

Additionally, categorical summaries for QTcB and QTcF values (<450 msec, ≥450 to 480 msec, ≥480 to <500 msec, and ≥500 msec) and QTcB and QTcF change from baseline values (0 to <30 msec, ≥30 to <60 msec, and ≥60 msec) will be presented by treatment group. The mean of the triplicate measurements will be used as the parameter in this summary table.

In this study, a larger proportion of QTc results were reported with an ‘other’ method of correction (rather than QTcB or QTcF). This will be handled as follows. For summaries of PCI, this will be assessed for QTc using QTcF values. In cases where QTcF is not reported and is unable to be derived, then PCI will be assessment using the value of QTc (other method of correction). Data will be presented separately for the two QT correction methods. For other summary tables (change from baseline in QTc and categories of QTc), data will be presented separately for QTc (other method of correction).

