11.5.3. Safety

ECG Parameters
ECG parameters will be collected in triplicate at each time point. The mean of the triplicate measurements will be calculated for each ECG parameter and used as the value for that time-point. For ECG findings and PCI criteria, all three ECGs will be considered and the worst case result will be summarised. For PCI criteria comparing to baseline, the mean of the triplicate measurements at baseline will be used as the baseline value.
ECG Findings
For the summary of ECG findings (where assessed in triplicate at each time-point) a 'worst case' assessment for each subject will be derived, so that the number of subjects and percentages sum to 100% within each time-point.
RR Interval

 RR is not collected for machine read ECG. IF RR interval (msec) is not provided directly, then RR can be derived as: 
 [1] If QTcB is machine read & QTcF is not provided, then: $RR = \left[\left(\frac{QT}{QTcB} \right)^2 \right] * 1000$ [2] If QTcF is machine read and QTcB is not provided, then: $RR = \left[\left(\frac{QT}{QTcF} \right)^3 \right] * 1000$

ECG Parameters

- If ECGs are manually read, the RR value preceding the measurement QT interval should be a collected value THEN do not derive the RR interval if it is available (i.e., collected on the eCRF). If the RR interval is not available then it may be derived using the formula above.

Corrected QT Intervals

- Where QTcB and/or QTcF are reported in the eCRF then these reported values should be used (with no re-derivation).
- When not entered directly in the eCRF, corrected QT intervals by Bazett's (QTcB) and Fredericia's (QTcF) formulas will be calculated, in msec, depending on the availability of other measurements. IF RR interval (msec) is provided or derived then missing QTcB and/or QTcF will be derived as:

$$QTcB = \frac{QT}{\sqrt{\frac{RR}{1000}}}$$

$$QTcF = \frac{QT}{3\sqrt{\frac{RR}{1000}}}$$

- If only QTc (other method of correction) is reported then QTcB and QTcF are unable to be derived. Then data for QTc (other method of correction) will be summarised. This will be presented as a separate parameter.

QTcF / QTcB Categories

- QTcB and QTcF values will be summarised using the following categories:
- Absolute: <450 msec; ≥450 to 480 msec; ≥480 to <500 msec; and ≥500 msec
- Change from baseline: 0 to <30 msec; ≥30 to <60 msec, and ≥60 msec.

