- The mean of the triplicate measurements at each visit will be used in these summaries.
- Data for QTc (other method of correction) will also be presented as a separate parameter in these summary tables.

Adverse Events

AE Density

- AE density, also referred to as event density, will be calculated as the number of events in a given period divided by the total person time on treatment (in years) of subjects at risk at the beginning of the same period. All AE densities will be presented per 100 person-years (by multiplying the above defined statistics by 100). i.e.:
- On-therapy AE density = 100 x number of on-therapy AEs/total person time on treatment (years)
- Note: see exposure derivations for total person time on treatment calculation.

AE's of Special Interest

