11.7.2. ECG

ECG Parameter	Units	Clinical Concern Range	
		Lower	Upper
Absolute			
Absolute QTc Interval	msec		≥ 500
Absolute PR Interval	msec	< 110	> 220
Absolute QRS Interval	msec	< 75	> 110
Absolute Heart Rate	bpm	< 50	> 120
Change from Baseline			
Increase from Baseline QTc	msec		≥ 60
Increase from Baseline PR Interval	msec		>50% when baseline PR ≤ 200 msec
Increase from Baseline QRS Interval	msec		>50% when baseline QRS ≤ 100 msec

Note: PCI will be assessed for QTc using QTcF values. In cases where QTcF is not reported and is unable to be derived, then PCI will be assessment using the value of QTc (other method of correction). Data will be presented separately for the two QT correction methods.

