3.38.	Safety		Summary Characteristics of On-therapy Investigator-Reported Injection Site Reactions by Anti-Albiglutide Antibody Status		SAC [1]
3.39.	Safety	AE1	Summary of On-therapy Investigator-Reported Systemic Allergic Reactions by SOC and PT		SAC [1]
3.40.	Safety		Summary of On-therapy Investigator-Reported Renal Impairment by SOC and PT		SAC [1]
3.41.	Safety		Summary of On-therapy Diabetic Ketoacidosis (DKA) identified by a Customised MedDRA Query by SOC and PT		SAC [1]
3.42.	Safety		Summary of On-therapy Appendicitis identified from a Customised MedDRA Query by SOC and PT		SAC [1]
3.43.	Safety		Summary of On-therapy Malignant Neoplasms identified from a Standard MedDRA Query by SOC and PT		SAC [1]
3.44.	Safety		Summary of On-therapy Liver Events identified from a Customised MedDRA Query by SOC and PT		SAC[1]
Laboratory: Chemistry					
3.45.	Safety	LB1	Summary of Chemistry Changes from Baseline by Visit	ICH E3	SAC [1]
3.46.	Safety	LB17	Summary of Chemistry Shifts from Baseline with Respect to Potential Clinical Importance (PCI) Criteria	ICH E3	SAC [1]

Safety : Tables					
No.	Population	IDSL / TST ID / Example Shell	Title	Programming Notes	Deliverable [Priority]
Laboratory: Hematology					
3.47.	Safety	LB1	Summary of Hematology Changes from Baseline by Visit	ICH E3	SAC [1]
3.48.	Safety	LB17	Summary of Hematology Shifts from Baseline with Respect to Potential Clinical Importance (PCI) Criteria	ICH E3	SAC [1]
Laboratory: Urinalysis					
3.49.	Safety	LB1	Summary of Urinalysis Changes from Baseline by Visit	ICH E3	SAC [1]
3.50.	Safety	UR3	Summary of Urinalysis Categorical Results	IDSL	SAC [1]
Laboratory: Hepatobiliary (Liver)					
3.51.	Safety	LIVER1	Summary of Liver Monitoring/Stopping Event Reporting	IDSL	SAC [1]
3.52.	Safety	LIVER10	Summary of Hepatobiliary Laboratory Abnormalities	IDSL	SAC [1]
ECG					
3.53.	Safety	EG1, GLP113121, Switch	Summary of ECG Findings by Visit	IDSL	SAC [1]
3.54.	Safety	EG2, per vitals/lab templates	Summary of ECG Changes from Baseline by Visit	IDSL	SAC [1]
3.55.	Safety	per vitals/lab templates	Summary of ECG Shifts from Baseline with Respect to Potential Clinical Importance (PCI) Criteria		SAC [1]
3.56.	Safety	CP_EG11, GLP113121, Switch	Summary of QTcB and QTcF ECG Results by Visit and Category	IDSL	SAC [1]

Safety : Tables					
No.	Population	IDSL / TST ID / Example Shell	Title	Programming Notes	Deliverable [Priority]

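### As SAP 8.2.3.2 is written, the ECG shift table (Table 3.55) compares a baseline mean of three readings with the worst of three afterwards, so unchanged subjects can appear to shift to abnormal

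*SAP*

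**What the plan says.** ECGs are recorded in triplicate at each scheduled time (Protocol 6.4.6). The Time and Events table places them at Baseline and at Weeks 4, 16, 28, 40, 52 and 64.

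For values of potential clinical importance (PCI), SAP 8.2.3.2 states: "For ECG findings and PCI criteria, all three ECGs will be considered and the worst case result will be summarised". It then adds: "The baseline value used for assessing PCI will be the mean of the triplicate measurements". SAP 11.5.3 repeats the first rule but narrows the second: "For PCI criteria comparing to baseline, the mean of the triplicate measurements at baseline will be used as the baseline value".

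The PCI limits in SAP 11.7.2 include "Absolute QTc Interval" of 500 msec or more and "Increase from Baseline QTc" of 60 msec or more. They also set absolute ranges for PR (110 to 220 msec), QRS (75 to 110 msec) and heart rate (50 to 120 bpm). The results go into Table 3.55, titled "Summary of ECG Shifts from Baseline with Respect to Potential Clinical Importance (PCI) Criteria".

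The QTc category tables (3.56 and 3.57) have the same 500 and 60 msec cut-points as their top categories but rest on a different value. SAP 8.2.3.2 says: "The mean of the triplicate measurements will be used as the parameter in this summary table". SAP 11.5.3 agrees: "The mean of the triplicate measurements at each visit will be used in these summaries".

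**The concern.** A shift table is read as change within the subject. That reading needs the same measurement rule before and after treatment starts. The worst of three readings lies further out than their mean even when nothing has changed, so using the mean only at baseline creates apparent movement from normal to abnormal.

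Safety data are descriptive (Protocol 8.3.5.4), so readers will judge the raw counts, and only about 17 subjects receive placebo. Two further matters follow. The two SAP sections could lead two programmers to build the baseline column of Table 3.55 differently. And one report could give two QTcF counts for what looks like the same criterion, with no planned note to explain the difference.

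**Working it through.** The plan states no rate for this point, so there is no figure to reproduce. Every mean and SD below is an assumption; the limits and the three readings per visit come from the SAP and protocol.

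**1. Which rule applies at baseline**

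| | SAP 8.2.3.2 | SAP 11.5.3 |
|---|---|---|
| PCI after baseline | worst of three | worst of three |
| Baseline, change criteria | mean of three | mean of three |
| Baseline, absolute limits | mean of three | not covered by the baseline sentence |

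The change criteria are asymmetric under both sections. The absolute limits are asymmetric under 8.2.3.2 and undetermined under 11.5.3.

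**2. Offset with no true change**

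The expected maximum of three normal readings is 0.85 within-visit SD above their mean. For QTcF with a within-visit SD of 5, 10 or 15 msec, the simulated offset is 4.2, 8.5 or 12.7 msec.

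**3. False net shift at one visit, absolute limits**

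Take QRS with mean 92 msec, between-subject SD 9, between-visit SD 3 and within-visit SD 4.

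- By the mean of three: SD = √(81 + 9 + 16/3) = 9.76. The proportion outside 75–110 is Φ(−17/9.76) + Φ(−18/9.76) = 4.08% + 3.26%, about 7.35% (7.37% by simulation).
- By the worst of three: 1 − E[{Φ((110 − X)/4) − Φ((75 − X)/4)}³] with X normal, mean 92, SD √90. This gives 15.7%.

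The mismatched rule therefore shows 7.4% abnormal at baseline and 15.7% later. Matched rules show no net shift: 7.4% to 7.4% by mean, or 15.7% to 15.7% by worst. The net excess is about 8.3 points, or 51 × 0.083 = 4.2 albiglutide and 17 × 0.083 = 1.4 placebo subjects at one visit.

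The same formulas over the assumed within-visit SDs:

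| Parameter (mean; between-subject/between-visit SD) | Within-visit SD | Outside limits, mean of three | Outside limits, worst of three |
|---|---|---|---|
| QRS (92; 9/3 msec) | 2, 4, 6 | 6.7%, 7.3%, 8.4% | 10.0%, 15.7%, 23.7% |
| PR (150; 20/6 msec) | 4, 8, 12 | 2.9%, 3.1%, 3.5% | 4.2%, 6.5%, 9.9% |
| Heart rate (68; 10/6 bpm) | 2, 4, 6 | 6.2%, 6.5%, 7.0% | 8.3%, 11.2%, 15.1% |

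**4. How much of the any-visit excess is the mismatch**

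For QRS with within-visit SD 4, the share of baseline-normal subjects abnormal at any of five on-therapy visits (Weeks 4 to 52) is:

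- mean on both sides: 10.9%
- worst on both sides: 23.7%
- mean at baseline, worst afterwards: 28.4%

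The total excess is 28.4 − 10.9 = 17.5 points. Of this, 28.4 − 23.7 = 4.7 points come from the mismatch and 23.7 − 10.9 = 12.8 from taking extremes over many readings.

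**5. QTcF in Table 3.55 against Tables 3.56 and 3.57**

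For the same subject, visit and correction, the maximum is at least the mean. Any value that reaches 500 msec, or a 60 msec rise, on the mean also reaches it on the worst reading. Table 3.55 can only be equal or higher.

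With mean 400, between-subject SD 18 and between-visit SD 10 msec, the no-change rate of a rise of 60 msec or more at any of six visits (Weeks 4 to 64), worst against mean, is:

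- within-visit SD 5: 0.04% against 0.01%
- within-visit SD 10: 0.72% against 0.06%
- within-visit SD 15: 4.9% against 0.4%

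The chance that at least one of 68 subjects is counted in Table 3.55 but not in Tables 3.56/3.57 is 1 − (1 − q)^68. With q = 0.040%, 0.677% and 4.73% for within-visit SDs of 5, 10 and 15, it is 3%, 37% and 96%. Over between-visit SDs of 8 to 15 and within-visit SDs of 5 to 20 it runs from 0.2% to 100%.

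**The case against.** The strongest reply is that Table 3.55 is a deliberately sensitive screen, openly described. A single extreme reading is worth flagging, and averaging would drop it from the table. The laboratory and vital-sign PCI tables also use a worst case in their any-visit rows. Most of the any-visit excess comes from that screening, as step 4 shows. This stands, and it is why the point does not require the sponsor to give up the worst-of-three rule. It does not answer the mismatch: the same rule can be used at baseline without losing any post-baseline flag.

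The second reply is that 11.5.3 may already confine the baseline mean to the change criteria. That is possible, but 8.2.3.2 is worded more broadly and the two sections need to agree.

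A reader might also infer three stronger things, and the documents do not support them.

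- **That a drug effect would be hidden or biased.** The rule is the same in both arms, there is no safety testing, and Table 3.54 reports change from baseline on triplicate means.
- **That Table 3.55 will disagree with Tables 3.56 and 3.57.** It differs only if a triplicate straddles a limit, which may not happen in about 68 subjects. The overlap covers QTcF or the other-correction QTc only, because PCI does not use QTcB.
- **That false QTc rises will be common.** A rate of 5.3% against 1.7% over five visits needs an assumed between-visit SD of 15 msec. At 10 msec, with a within-visit SD of 5 to 10, it is about 0.05–0.6% against 0.01–0.06%.

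**Conclusion.** The point holds, at minor severity. As 8.2.3.2 is written, Table 3.55 compares two different statistics and will tend to show shifts to abnormal in subjects who have not changed. It matters mainly for QRS, PR and heart rate. Under the assumed SDs, the false net shift at one visit is about 3 to 15 percentage points for QRS, 1 to 6 for PR and 2 to 8 for heart rate. For QTcF the effect is small unless within-visit or between-visit variability is high, and the discrepancy with Tables 3.56 and 3.57 can go in one direction only.

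The mismatch and the difference between the two sections are in the SAP text. The sizes are not: all rest on assumed normal variation. The point covers PCI only. ECG findings (Table 3.53) take the worst case at each time-point under 11.5.3, so they do not share the mismatch.

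**What to change.** Give SAP 8.2.3.2 and 11.5.3 the same wording, and use one summary on both sides of Table 3.55.

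- **Absolute limits:** either keep worst-of-three and apply it at baseline too, or use the triplicate mean at baseline and at every later visit. In the second case, let any single reading beyond a limit still trigger inclusion in Listing 76.
- **QTc rise of 60 msec or more:** compute it on triplicate means, as Table 3.57 does. Otherwise footnote Table 3.55 to say that its counts set the worst reading against a mean baseline and may exceed those in Tables 3.56 and 3.57.

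The cost is about one sentence in each section, plus a footnote if that route is chosen. Worst-of-three at baseline classes more subjects as abnormal before treatment. Using the mean throughout moves isolated extreme readings from the table to the listing.

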8.3. Pharmacokinetic Analyses

8.3.1. Overview of Planned Pharmacokinetic Analyses

The pharmacokinetic (PK) analyses will be based on the “Pharmacokinetic” population, unless otherwise specified.

Albiglutide plasma concentration data will be summarised for the albiglutide group. Descriptive summary statistics will be presented for each nominal scheduled visit where samples were collected (Week 4, Week 6, Week 8 and Week 16).

Mean (sd) plasma concentration versus scheduled time profiles and median plasma concentration versus scheduled time profiles will be presented in separate figures on both linear and semi-logarithmic scales.

A scatter plot of individual plasma concentrations versus scheduled time will be produced. In addition to individual plasma concentrations, this will also show a box and whisker plot of median and appropriate percentiles.

There will be no statistical analysis of PK parameters.

Table 9 provides an overview of the planned analyses, with full details being presented in Appendix 13: List of Data Displays.

Table 9 Overview of Planned Pharmacokinetic Analyses

Parameter	Untransformed				Log-Transformed			
	Summary		Individual		Summary		Individual	
	T	F	F	L	T	F	F	L
Albiglutide plasma concentration	Y	Y ^[1]		Y				

NOTES :

- T = Table, F = Figure, L = Listings, Y = Display generated.
- Summary = Represents TFL related to any summaries (i.e. descriptive statistics) of the observed raw data.
- Individual = Represents FL related to any displays of individual subject observed raw data.
- [1] Mean (Linear and Semi-Log on same display) and Median (Linear and Semi-Log on same display) plots will be created. A box and whisker/scatter plot will also be produced.

8.3.2. Pharmacokinetic Parameters**8.3.2.1. Deriving Pharmacokinetic Parameters**

- Refer to [Appendix 4](#): Data Display Standards & Handling Conventions (Section [11.4.3](#) Reporting Process & Standards).
- The pharmacokinetic parameters will be calculated by standard non-compartmental analysis according to current working practices and using Win Nonlin.
- The population pharmacokinetic parameters will be calculated by pop PK modelling in NONMEM.
- All calculations of non-compartmental parameters will be based on actual sampling times.
- Pharmacokinetic parameters described in [Table 10](#) will be determined from the albiglutide plasma concentration-time data, as data permits.
- All PK parameters described in [Table 10](#) will be derived and reported by the GSK CPMS group.

Table 10 Derived Pharmacokinetic Parameters

Parameter	Parameter Description
AUC (0-t)	Area under the concentration-time curve from time zero to the time of the last quantifiable concentration (C(t))
AUC (0-t)/t	Average concentration over the time period
Cmax	Maximum observed concentration, determined directly from the concentration-time data.
Pop.CL/F	Population apparent clearance
Pop.V/F	Population apparent volume of distribution
Pop.Ka	Population first-order absorption rate constant

NOTES:

- Additional parameters may be included as required.

8.3.3. Population Pharmacokinetic (PopPK) Analyses

- The primary goal of this analysis is to characterize the population pharmacokinetics of albiglutide administered subcutaneously in subjects with NOT1DM.
 - The influence of subject demographics, baseline characteristics, including disease activity, and co-medication on the pharmacokinetics of albiglutide in this population will be investigated.
- A summary of the planned population pharmacokinetic analyses are outlined below:
 - Drug plasma concentration-time data will be subjected to nonlinear mixed effects modelling using the program NONMEM.
 - Individual post-hoc estimated PK parameters will be summarised descriptively.
 - To support this analysis a NONMEM file will be generated.
 - The details for the dataset specifications are provided in [Appendix 10: Population Pharmacokinetic Analyses](#) with detailed methodology for the analysis.

The population PK parameters (e.g., CL/F, V/F, and Ka) will be summarised for the albiglutide group. The relationship between albiglutide PK parameters and subject covariates of interest will be evaluated in the population PK model. All population PK analyses will be performed and reported by the GSK CPMS group.

8.4. Pharmacokinetic / Pharmacodynamic Analyses

In a change to the planned analysis specified in the protocol, exploratory endpoints will not be summarised or presented graphically. Therefore, PK/PD analyses specified under the exploratory objectives section of the protocol will not be performed. There will be no data listing for this exploratory endpoint.

In a change to the planned analysis specified in the protocol, analysis of the secondary endpoint of 'population estimates of PD parameters (e.g., Emax, EC₅₀), associated inter-subject variability and residual error if permitted by the data' will not be conducted.

